- [42] Have received systemic non-biologic PsO therapy (including, but not limited to, oral psoralens and ultraviolet A [PUVA] light therapy; cyclosporine; corticosteroids; methotrexate [MTX]; oral retinoids; mycophenolate mofetil; thioguanine; hydroxyurea; sirolimus; azathioprine; fumaric acid derivatives; or 1,25 dihydroxy vitamin D3 and analogues) or phototherapy (including either oral and topical PUVA light therapy, ultraviolet B [UVB] or self-treatment with tanning beds or therapeutic sunbathing) within 4 weeks prior to baseline (Week 0; Visit 2); or had topical PsO treatment (including, but not limited to, corticosteroids, anthralin, calcipotriene, topical vitamin D derivatives, retinoids, tazarotene, emollients and other non-prescription topical products containing urea, >3% salicylic acid, or alpha- or beta-hydroxyl acids, and medicated shampoos [e.g., those that contain >3% salicylic acid, corticosteroids, coal tar, or vitamin D3 analogues]) within the previous 2 weeks prior to baseline (Week 0; Visit 2).

Exceptions: class 6 (mild, such as desonide) or class 7 (least potent, such as hydrocortisone) topical steroids will be permitted for use limited to the face, axilla, and/or genitalia.

- [43] Have pustular, erythrodermic, and/or guttate forms of PsO.
- [44] Had a clinically significant flare of PsO during the 12 weeks prior to baseline (Week 0; Visit 2).
- [45] Have allergy to rubber or latex.

PsA Participants

- [46] Have used conventional synthetic disease-modifying antirheumatic drug (csDMARDs) other than MTX, leflunomide, sulfasalazine, or cyclosporine in the 8 weeks prior to baseline (Week 0; Visit 2).

Have discontinued MTX, sulfasalazine, or cyclosporine within 12 weeks prior to baseline (Week 0; Visit 2).

If taking MTX, leflunomide, sulfasalazine, or cyclosporine, must have been treated for at least 12 weeks prior to baseline *and* on a stable dose for at least 8 weeks prior to baseline, as follows: oral or parenteral MTX = 10 to 25 mg/week; leflunomide = 20 mg/day; sulfasalazine = up to 3 g/day; or cyclosporine up to 5 mg/kg/day. The dose of these allowed concomitant medications must remain unchanged during the study periods of the unless changes are required for safety issues. Local standard of care should be followed for concomitant administration of folic acid with MTX.

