[47] Are currently receiving treatment with any biologic or small molecule therapy for PsA or PsO, including investigational therapies (such as, but not limited to, a TNFi, IL-1 receptor antagonists, IL-6 inhibitor, anti-IL-12/23p40, T cell or B cell targeted therapies, phosphodiesterase [PDE] 4 inhibitors, or Janus kinase [JAK] inhibitors), or have received denosumab.

[48] Have received treatment with IL-17 or IL12/23 targeted Mab therapy.

[49] Have used disease-modifying antirheumatic drug (DMARDs) other than MTX, leflunomide, sulfasalazine, or hydroxychloroquine (e.g., gold salts, cyclosporine, azathioprine, dapsone, 6-mercaptopurine, mycophenolate mofetil, or any other immunosuppressive agents) in the 8 weeks prior to baseline (Week 0, Visit 2).

Have discontinued MTX or sulfasalazine within the 8 weeks prior to baseline, or hydroxychloroquine within 12 weeks prior to baseline.

If taking MTX, leflunomide, sulfasalazine, or hydroxychloroquine must have been treated for at least 12 weeks prior to baseline and on a stable dose for at least 8 weeks prior to baseline, as follows: oral or parenteral MTX = 10 to 25 mg/week; leflunomide = 20 mg/day; sulfasalazine = up to 3 g/day; or hydroxychloroquine = up to 400 mg/day. The dose of these allowed concomitant medications must remain unchanged until W12 of the study, unless changes are required for safety issues. Local standard of care should be followed for concomitant administration of folic acid with MTX.

[50] Are receiving treatment with more than 1 conventional DMARD (MTX, leflunomide, sulfasalazine, or hydroxychloroquine) at study entry.
Note: Under no circumstances will simultaneous use of MTX and leflunomide be allowed at any time during the study for safety reasons.

[51] Have discontinued leflunomide within 4 weeks prior to baseline or have received leflunomide from 4 to 12 weeks prior to baseline (Week 0, Visit 2) and have not undergone a drug elimination procedure.

[52] Use of oral corticosteroids at average daily doses of >10 mg/day of prednisone or its equivalent, or use of variable doses of any oral corticosteroids, within 4 weeks prior to baseline (Week 0, Visit 2).

- [53] Have received any parenteral glucocorticoid administered by intraarticular, intramuscular, or intravenous (IV) injection within 6 weeks prior to baseline (Week 0, Visit 2), or for whom a parenteral injection of glucocorticosteroids is anticipated until W12 of the study.

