- [54] Concomitant use of nonsteroidal anti-inflammatory drug (NSAIDs), including cyclooxygenase-2 (COX-2) inhibitors, unless the patient is on a stable dose for at least 2 weeks prior to baseline (Week 0, Visit 2).
- [55] Use of any opiate analgesic at average daily doses of >30 mg/day of morphine or its equivalent or use of variable doses of any opiate analgesic within 6 weeks prior to baseline (Week 0, Visit 2).
- [56] Have a diagnosis of other inflammatory arthritic syndromes such as rheumatoid arthritis (RA), ankylosing spondylitis, reactive arthritis, or enteropathic arthritis.
- [57] Have active Crohn's disease or active ulcerative colitis.
- [58] Have diagnosis of fibromyalgia.
- [59] Have a chronic pain condition that would confound evaluation of the patient.
- [60] Have evidence of active vasculitis or uveitis.
- [61] Have had surgical treatment of a joint within 8 weeks prior to baseline or will require such up to Week 24.

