Abbreviations: CRS/CRP = clinical research scientist/clinical research physician; csDMARD = conventional synthetic disease-modifying antirheumatic drug; IL = interleukin; MTX = methotrexate; NSAID = nonsteroidal anti-inflammatory drug; PASI = Psoriasis Area and Severity Index; PsA = psoriatic arthritis; PsO = plaque psoriasis; PUVA = psoralen and ultraviolet A; RNA = ribonucleic acid; sPGA = static Physician Global Assessment; UVB = ultraviolet B.

^a Mason et al. 2002.

Additional drugs are to be avoided during the study unless required to treat an AE or for the treatment of an ongoing medical problem. If the need for concomitant medication arises, the investigator should base decisions on the participant and clinical factors. Any additional medication (including the limited use of therapeutic agents which, if used under treatment regimens other than for treating an AE or for appropriate medical management, might be considered PsO/PsA therapies) whether prescription or over-the-counter, used at baseline (Week 0, Visit 2) and/or during the course of the study, must be documented with the start and stop dates on the Concomitant Medications CRF.

Participants will maintain their usual medication regimen for other concomitant diseases throughout the study unless those medications are specifically excluded in the protocol.

Participants taking concomitant medications should be on stable doses at the time of baseline (Week 0, Visit 2) and should remain at a stable dose throughout the study, unless changes need to be made for an AE or for appropriate medical management. Other medications may be allowed if approved by the Sponsor or its designee.

Participants should be instructed to consult the investigator or other appropriate study personnel at the site before taking any new medications or supplements. Any changes in medications not addressed above should be discussed by the investigator with the Sponsor.

7. Discontinuation of Study Intervention and Participant Discontinuation/Withdrawal

Discontinuation of specific sites or of the study as a whole are handled as part of Section 10.1, Section 10.1.7.

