8.1. Efficacy Assessments

The secondary endpoints for PsO group are:

- Proportion of participants who achieve the following PASI scores: PASI 75 (defined as 75% improvement from baseline in PASI) at Week 12
- Proportion of participants with an sPGA score of 0 or 1 (0, 1) at Week 12.

The secondary endpoints for PsA group are:

- Proportion of PsA participants achieving ACR20 at Week 24.

Exploratory endpoints include, but not limited to, DAS-28-CRP and ACR individual components.

For PsO participant who also meet active PsA definition, both PsA and PsO outcomes will be collected for that participant. Likewise, to fulfill the study objective, PsO outcomes will be collected among all the PsA participants with 3% or more BSA of PsO ([Table RHCZ.8.1](#)).

Table RHCZ.8.1. Efficacy Assessments

Assessments	PsO Participants with No Active PsA	PsA Participants with	
		≥3% BSA of PsO	<3% BSA of PsO
Clinician assessments	
 • PASI • Percentage of BSA - Psoriasis • sPGA • PGA Disease Activity VAS 	
 • TJC/SJC (68/66 joints) • PGA of Disease Activity VAS -Psoriasis • PGA of Disease Activity VAS - PsA • PASI • Percentage of BSA - Psoriasis • sPGA • DAS28 - CRP^a • ACR20/50/70^a 	
 • TJC/SJC (68/66 joints) • PGA of Disease Activity VAS - PsA • DAS28 - CRP^a • ACR20/50/70^a
Patient assessments	
 • Patient's Global Assessment of disease activity VAS - Psoriasis 	
 • HAQ-DI • PsA Pain assessment question included in HAQ-DI • Patient's Global Assessment of Disease Activity VAS - PsA • Patient's Global Assessment of Disease Activity VAS - Psoriasis 	
 • HAQ-DI • PsA Pain assessment question included in HAQ-DI • Patient's Global Assessment of Disease Activity VAS - PsA

Abbreviations: ACR20/50/70 = 20%/50%/70% improvement in American College of Rheumatology response criteria; BSA = body surface area;

CRP = C-reactive protein; DAS28 = Disease Activity Score-28; HAQ-DI = Health Assessment Questionnaire – Disability Index; PASI = Psoriasis Area and Severity Index; hs-CRP = high-sensitivity C-reactive protein; PGA = Physician's Global Assessment; PsA = psoriatic arthritis; PsO = plaque psoriasis; SJC = swollen joint count; sPGA = static Physician's Global Assessment; TJC = tender joint count, V = visit; VAS = visual analog scale.

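### Minor: exclusion [53] looks ahead for parenteral glucocorticoid injections only to Week 12, although the PsA endpoint, ACR20, is read at Week 24

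*Protocol*

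**What the plan says.** **Eligibility (Protocol 5.2, PsA Participants).** Exclusion [53] has two parts. The first bars intra-articular, IM or IV glucocorticoid in the 6 weeks before baseline. The second bars those "for whom a parenteral injection of glucocorticosteroids is anticipated until W12 of the study". No reason for the Week 12 limit is given.

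**Endpoint (Protocol 8.1).** The PsA group has one secondary endpoint: "Proportion of PsA participants achieving ACR20 at Week 24". Week 12 is the time point of the two PsO secondary endpoints.

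**Other dates in the same list.**
- [61], joint surgery, looks ahead to the endpoint: "Have had surgical treatment of a joint within 8 weeks prior to baseline or will require such up to Week 24".
- [46], conventional DMARD doses, covers the study: "The dose of these allowed concomitant medications must remain unchanged during the study periods".
- [49], also on DMARD doses, stops at Week 12: "The dose of these allowed concomitant medications must remain unchanged until W12 of the study, unless changes are required for safety issues".

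**On-study rules (Protocol 6.8).** Concomitant medications "should remain at a stable dose throughout the study, unless changes need to be made for an AE or for appropriate medical management". Also: "Additional drugs are to be avoided during the study unless required to treat an AE or for the treatment of an ongoing medical problem". Any such additional medication "must be documented with the start and stop dates on the Concomitant Medications CRF".

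**The concern.** An exclusion that looks ahead for a confounding treatment should reach at least as far as the outcome that the treatment could distort. A systemic glucocorticoid can improve tender and swollen joint counts, pain, the global assessments and CRP, which are all components of ACR20. [53] stops 12 weeks short of the only PsA secondary endpoint, while [61] does not.

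The study has one arm, so no comparator would absorb the effect of an IM or IV injection given shortly before Week 24. It would be counted as response to ixekizumab, and the error would run upward. At stake is the reading of one descriptive proportion.

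**Working it through.** The question is mainly one of text, so the relevant sections are set side by side.

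1. **Who passes [53].** An injection anticipated before Week 12 excludes the candidate. One anticipated between Week 12 and Week 24 does not. ACR20 is read at the end of that second interval.

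2. **What 6.8 does with such an injection.** The stable-dose rule and the rule against additional drugs have no Week 12 cut-off; they are no looser after Week 12 than before. In Table RHCZ.6.3, corticosteroids appear in the systemic nonbiologic row, which PsA participants may use at a stable dose. A one-off injection hardly fits that condition. Two points keep the restriction from being complete. The table has no row for parenteral glucocorticoid. And 6.8 refers back to the entry criteria for what PsO and PsA therapy is allowed, where the only forward-looking line on these injections ends at Week 12.

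3. **What happens when a prohibited agent is needed.** Under 7.2, a participant who needs a prohibited, effective therapy leaves the study before it starts. Under 9.3.1, stopping study treatment before the time point makes the participant a nonresponder.

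4. **What is left.** Suppose an IM or IV injection is given and study treatment continues. The four nonresponse triggers in 9.3.1 are: response criteria not met, missing data, treatment discontinued, and no postbaseline observation. Glucocorticoid use is not among them. Section 9.2 keeps participants who depart from the protocol in the Active PsA mITT population. Such a participant can count as a Week 24 responder.

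5. **Which part of this [53] causes.** Only injections already anticipated at entry for Weeks 12 to 24. Injections given under the 6.8 exceptions (an adverse event, an ongoing medical problem, appropriate medical management) are generally not foreseen at entry. They can occur just as well in Weeks 0 to 12, and no date in [53] would reach them.

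6. **Intra-articular injections.** Section 8.1.2 drops an injected joint from evaluation for the rest of the study, so the point is limited to the IM and IV routes.

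**Scale, not an estimate.** The plan offers no figure on this point. Its one reproducible sample-size figure, 250 × 0.90 = 225 completers (9.7), checks and plays no part here. Inputs: 100 planned PsA participants (9.7) and the normal-approximation 95% CI named in 9.5.3.
- One participant changed from nonresponder to responder moves ACR20 by 1/100 = 1.0 percentage point.
- The CI half-width is 1.96 × √(p(1 − p)/100). With p assumed, because the protocol states no expected ACR20 rate:

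| Assumed ACR20 | Half-width (points) |
|---|---|
| 40% | 9.60 |
| 50% | 9.80 |
| 60% | 9.60 |
| 70% | 8.98 |

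How many participants would be changed in this way cannot be derived from the protocol.

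**The case against.** The strongest reply is that [53] is an entry criterion, checked at screening and baseline, and does not govern treatment during the study. Section 6.8 does, for the whole study, and 7.2 with 9.3.1 deals with prohibited use. An investigator who knows at entry that an off-protocol injection will be needed can also use [36], the general criterion on conditions that prevent completing the protocol. The injections most likely to occur, those under the 6.8 exceptions, would be untouched by a later date in [53]. Week 12 also appears in [49], so it is not an isolated slip. Finally, a supportive analysis is something the protocol leaves to the SAP.

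Most of this stands, and it sets the size of the point. It does not remove the mismatch. Nothing explains why the steroid look-ahead stops at Week 12 when the surgery look-ahead reaches Week 24, and the eligibility date can only be corrected in the protocol. The appearance of Week 12 in [49] shows that the dates in this list are mixed; it is not a reason for the date in [53].

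Two stronger readings are tempting. A reader might infer that IM or IV glucocorticoid is freely allowed after Week 12, leaving half of the 24 weeks unprotected. The document does not support this, because the 6.8 rules run throughout. A reader might also infer that the Week 24 ACR20 will be materially inflated. No injection rate is given and nothing indicates that candidates with such planned injections exist, so no number of false responders can be defended.

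**Conclusion.** The point holds as a small inconsistency between an entry criterion and the endpoint it should protect. A PsA candidate with an IM or IV glucocorticoid injection already anticipated for Weeks 12 to 24 is not excluded by [53], although ACR20 is read at Week 24. Sections 6.8, 7.2 and 9.3.1 limit most such use.

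The direction of any bias is upward. Its size cannot be estimated from the protocol and is probably small. It concerns one descriptive secondary proportion in a single-arm safety study without hypothesis tests; the primary safety endpoint is unaffected. The conclusion assumes that a recipient may stay on ixekizumab and remain in the Active PsA mITT population, which 9.2 and 9.3.1 allow. This is an inexpensive improvement, not a flaw that threatens the study.

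**What to change.** In [53], replace W12 by Week 24 as the end of the look-ahead, in line with [61] and the endpoint. The cost is a change to one criterion and possibly slightly fewer eligible PsA candidates.

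Optionally, report one supportive Week 24 ACR20 that counts any participant given IM or IV glucocorticoid during Weeks 0 to 24 as a nonresponder. This covers the injections under the 6.8 exceptions, which [53] cannot reach and which 9.3.1 does not treat as nonresponse. It needs no new data, because 6.8 already requires start and stop dates for such medication. The supportive rate may come out slightly lower than the main one. If the SAP already contains such an estimate, only the change to [53] is needed.

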5.3. Lifestyle Considerations

See inclusion criteria [2] in Section [5.1](#) for birth control requirements.

5.4. Screen Failures

A screen failure occurs when a participant who consents to participate in the clinical study is not subsequently enrolled in the study. A minimal set of screen failure information is required to ensure transparent reporting of screen failure participants to meet the Consolidated Standards of Reporting Trials (CONSORT) publishing requirements and to respond to queries from regulatory authorities. Minimal information includes demography, screen failure details, eligibility criteria, and any SAE.

Individuals may be re-screened only once in the following circumstances:

- Patients who test positive for latent TB at screening and have undergone documented subsequent treatment for at least 4 weeks (more details in Section [8.2.7](#)).
- Other reasons for rescreening must be discussed, approved and documented by the Lilly Medical Team (clinical research scientist [CRS]/clinical research physician [CRP]).

5.5. Criteria for Temporarily Delaying Enrollment/Administration of Study Intervention of a Participant

Dates of subsequent study visits should not be modified according to the delay of the injection of the missed scheduled dose.

6. Study Intervention(s) and Concomitant Therapy

Study intervention is defined as any investigational intervention(s), marketed product(s), placebo, or medical device(s) intended to be administered to/used by a study participant according to the study protocol.

6.1. Study Intervention(s) Administered

Table RHCZ.6.1. Treatment Regimens

Treatment Group	Starting Dose W0	Dose W2-W10	Dose ^a W12-W20
Ixekizumab for 
 • PsO participants with no active PsA • PsA participants who meet criteria for moderate-to-severe PsO 	Ixekizumab 80 mg × 2 SC (total of 160 mg)	Ixekizumab 80 mg SC Q2W at W2, 4, 6, 8, and 10	Ixekizumab 80 mg SC Q4W at W12, 16, and 20
Ixekizumab for PsA participants who do not meet criteria for moderate-to-severe PsO	Ixekizumab 80 mg × 2 SC (total of 160 mg)		Ixekizumab 80 mg SC Q4W at W4, 8, 12, 16, and 20

Abbreviations: PsA = psoriatic arthritis; PsO = psoriasis; Q2W = every 2 weeks; Q4W = every 4 weeks; SC = subcutaneous injection; W = week.

^a No dose is given at W24; therefore, W24 is not included in this table.

Note: When the dosing is scheduled at home (for PsO participants with no active PsA and PsA participants who meet criteria for moderate-to-severe PsO: W2, W6, W10, W16, and W20; for PsA participants who do not meet criteria for moderate-to-severe PsO: W16 and W20), the participants or care givers will administer the provided ixekizumab prefilled syringes.

The investigator or his/her designee is responsible for the following:

- explaining the correct method of dose administration to the participant or participant's caregiver;
- explaining the correct use of the investigational agent(s) to site personnel/legal representative;
- verifying those instructions are followed properly;
- maintaining accurate records of study intervention dispensing and collection; and
- returning all unused medication to Lilly or its designee at the end of the study

During study visits, the investigator or his/her designee will administer the ixekizumab prefilled syringes to the participant. When the dosing is scheduled at home, the participants or care givers will administer the provided ixekizumab prefilled syringes.

Note: In some cases, sites may destroy clinical trial material if during the investigator site selection, the evaluator has verified and documented that the site has appropriate facilities and written procedures for disposing of clinical trial materials.

Induction Dosing Period (Period 2) (Table RHCZ.6.2)

- At Week 0, a 160-mg starting dose of ixekizumab (two 80-mg injections), followed by ixekizumab 80 mg Q2W from Weeks 2 through 12 for PsO participants with no active PsA and PsA participants who meet criteria for moderate-to-severe PsO.
- At Week 0, a 160-mg starting dose of ixekizumab (two 80-mg injections), followed by ixekizumab 80 mg Q4W from Weeks 4 through 12 for PsA participants who do not meet the criteria for moderate-to-severe PsO participants.

Maintenance Period (Period 3) (Table RHCZ.6.2)

- Ixekizumab 80 mg Q4W (i.e., at Weeks 16 and 20).

Table RHCZ.6.2 presents the number of injections administered at each study week, for each dosing period.

Table RHCZ.6.2. Dosing Summary for the Induction and Maintenance Periods

Dosing Period	Study Week	Ixekizumab Treatment Group ^a	
		Ixekizumab (80 mg)	
		PsO Participants with no active PsA and PsA Participants Who Meet Criteria for Moderate-to-Severe PsO ^b	PsA Participants Who Do Not Meet Criteria for Moderate-to-Severe PsO ^c
Induction Dosing Period 2	0	2 ^a	2 ^a
	2	1	-
	4	1	1
	6	1	-
	8	1	1
	10	1	-
	12	1	1
Maintenance Period 3	16	1	1
	20	1	1
	24	-	-

Abbreviations: PsA = psoriatic arthritis; PsO = psoriasis; Q2W = every 2 weeks; Q4W = every 4 weeks; Q8W = every 8 weeks; SC = subcutaneous.

^a A starting dose of 160 mg (Week 0) of ixekizumab will be given as 2 SC injections at Week 0.

^b For PsO participants with no active PsA and PsA participants who meet criteria for moderate-to-severe PsO, during the Induction Dosing Period, ixekizumab (80 mg) will be given as 1 SC injection Q2W (i.e., Weeks 2, 4, 6, 8, 10, and 12). During the Maintenance Period, ixekizumab (80 mg) will be given as 1 SC injection Q4W (i.e., Weeks 16 and 20).

^c For PsA participants who do not meet criteria for moderate to severe PsO, ixekizumab (80 mg) will be given as 1 SC injection Q4W (i.e., Weeks 4, 8, 12, 16, and 20).

